5.1 Screening data

Screening data is not captured in the EDC.

5.2 Eligibility

Subjects fulfilling all of the following inclusion criteria are eligible for the study:

- Informed Consent as documented by signature
- Age 18 or older
- Currently smokes 5 or more cigarettes per day, for a least 12 months
- Willing to try to quit smoking within the next 3 months
- Persons providing a valid phone number, a valid email address and/or a valid postal address.

The presence of any one of the following exclusion criteria will lead to exclusion of the subject:

- Known hypersensitivity or allergy to contents of the e-liquid
- Participation in another study with investigational drug within the 30 days preceding the baseline visit and during the present study where interactions are to be expected
- Women who are pregnant or breast feeding
- Intention to become pregnant during the course of the study
- Persons having used ENDS or tobacco heating systems regularly in the 3 months preceding the baseline visit
- Persons having used nicotine replacement therapy (NRT) or other medications with demonstrated efficacy as an aid for smoking cessation such as varenicline or bupropion within the 3 months preceding the baseline visit
- Persons who cannot attend the 6- month follow-up visit for any reason
- Persons who cannot understand instructions delivered in person or by phone, or otherwise unable to participate in study procedures

5.3 Recruitment

A CONSORT patient flow diagram will be drawn following the CONSORT 2010 standards (<http://www.consort-statement.org/consort-2010>).

The flow chart will consider specifically:

- N assessed for eligibility
- N not eligible (with reasons)
- N randomized

CTU Bern	SAP for: ESTxENDS	Version: 4-02.0	
CTU Bern	Template: Statistical Analysis Plan (SAP)	Version: 03	
	Code: CS_STA_TEM-11	Valid from: 28-02-2019 5.6.2023	Page 12 of 27

- Ns allocated to intervention and control
- Ns not receiving allocated intervention
- Ns lost to follow-up (with reasons)
- Ns analysed
- Ns excluded from primary analysis (with reasons)

5.4 Baseline patient characteristics

Please note: P-values, standard errors, and confidence intervals are not shown in baseline tables since any significant difference can be explained by the play of chance if the randomization was performed properly.

Table 2: Baseline table.

Description	form	Variable	Type
Demography			
Alter	eligibility	ic_age	Continuous: Jahre
Geschlecht	demographics	gender	Categorical: Männlich, Weiblich, Trans
Zivilstand	demographics	marital_status	Categorical: Ledig, Verheiratet, Verwitwet, Geschieden, gerichtlich getrennt, registrierte Partnerschaft, aufgelöste registrierte Partnerschaft
Arbeitssituation	demographics	profession	Categorical: Vollzeitbeschäftigt, Teilzeitbeschäftigt, Selbstständig, Hausfrau/Hausmann, In Ausbildung (Lehre, Studium), Auf Arebitssuche, Andere
Höchster Bildungsabschluss	demographics	education	Categorical: Obligatorische Schule, Lehre, Gymnasiale Maturität/Berufsmaturität, Höhere Fachschule/Pädagogische Hochschule, Universitärer Abschluss, Keine, Andere
Medical history			
Medication	medication	med_yn, med_name	Binary: yes – no If yes free text to be categorized according to categories of use (most prevalent ones).
Arztbesuch in letzten 6 monaten	hospitalization	med_visit_6m	Binary: yes – no If yes 4 additional questions
Hospitalisation in letzten 6 monaten	hospitalization	hosp_stay_6m	Binary: Anzahl
Notfallstation in letzten 6 monaten	hospitalization	hosp_emergency_6m	Binary: yes – no If yes 3 additional questions

CTU Bern	SAP for: ESTxENDS	Version: 4-02.0
----------	-------------------	---------------------------------

CTU Bern	Template: Statistical Analysis Plan (SAP)	Version: 03	
	Code: CS_STA_TEM-11	Valid from: 28-02-2019 5.6.2023	Page 13 of 27

Description	form	Variable	Type
Tagesklinik in letzten 6 Monaten	hospitalization	hosp_day_6m	Binary: yes – no If yes 1 additional question
Leiden Sie momentan an einer Infektion, Fieber oder einer akuten Erkrankung?	healthstatus	hs_current	Binary: yes – no
Allergien	healthstatus	allergy	Binary: yes – no
Bluthochdruck	healthstatus	hypertension	Binary: yes – no
Hypercholesterinämie	healthstatus	hypercholesterol	Binary: yes – no
Diabetes	healthstatus	diabetes	Binary: yes – no
früherer Herzinfarkt	healthstatus	cardiovascular1	Binary: yes – no
Perkutane koronare Intervention	healthstatus	pci	Binary: yes – no If yes categorical
Koronararterien-Bypass	healthstatus	cabg	Binary: yes - no
Herzinsuffizienz (in Behandlung, frühere Hospitalisation)	healthstatus	cardiovascular3	Binary: yes - no
Herzklappenoperation	healthstatus	valve_op	Binary: yes - no
Transitorische ischämische Attacke in der Vorgeschichte	healthstatus	tia	Binary: yes - no
Angina pectoris	healthstatus	cardiovascular2	Binary: yes – no
Periphere arterielle Verschlusskrankheit der unteren Extremitäten	healthstatus	arterial_lower	Binary: yes – no
Andere arterielle Verschlusskrankheiten	healthstatus	arterial_other	Binary: yes – no
Schlaganfall	healthstatus	stroke	Binary: yes – no If yes categorical
Andere Herzgefässerkrankungen	healthstatus	cardiovas_other	Binary: yes – no
Lungenembolie	healthstatus	pe	Binary: yes – no
Tiefe Venenthrombose	healthstatus	dvt	Binary: yes – no
COPD	healthstatus	copd	Binary: yes – no
Chronische Bronchitis	healthstatus	chronic_bronch	Binary: yes – no
Asthma	healthstatus	asthma	Binary: yes – no
Obstruktives Schlafapnoesyndrom	healthstatus	osa	Binary: yes – no If yes categorical
Andere Lungenerkrankungen	healthstatus	pulmonary_other	Binary: yes – no
Krebs	healthstatus	cancer	Binary: yes – no
Andere Krankheiten	healthstatus	disease_other	Binary: yes – no
Andere wichtige gesundheitliche Ereignisse in der Vorgeschichte (z.B. Operationen)	healthstatus	med_hist_other	Binary: yes – no
Wie schätzen Sie Ihren Gesundheitszustand im Allgemeinen ein	healthstatus	health_perception	Categorical
Herzinfarkt oder Angina pectoris bei Verwandten 1. Grades?	healthstatus	hrtattack_angina	Binary: yes – no

CTU Bern	SAP for: ESTxENDS	Version: 1-02_0
----------	-------------------	---------------------------------

CTU Bern	Template: Statistical Analysis Plan (SAP)	Version: 03
	Code: CS_STA_TEM-11	Valid from: 28-02-2019 5.6.2023

Description	form	Variable	Type
Schlaganfall bei Verwandten 1. Grades?	healthstatus	genetic_stroke	Binary: yes – no
Respiratory symptoms*			
CAT	Respiratory symptoms	sum of all items (q1 to q8)	continuous (score)
MMRC	Respiratory symptoms	q10 if q9 == yes	ordinal (score)
COPD	Respiratory symptoms	q1_copd	Binary: yes – no
Asthma test			
ECRHS	asthma	q1_ecrhs to q7_ecrhs	continuous (score, number of yes)
ACT	asthma	q1 to q5	continuous (score)
MINNESOTA NICOTINE WITHDRAWAL SCALE	withdrawal symptoms	q1 to q15	continuous (score)
Depressed	withdrawal symptoms	q3	ordinal
Irritable	withdrawal symptoms	q1	ordinal
Restless	withdrawal symptoms	q2	ordinal
Hungry	withdrawal symptoms	q5	ordinal
Poor concentration	withdrawal symptoms	q4	ordinal
Lab values			
Metabolites of nicotine:			
Anabasine	To be defined	To be defined	Continuous
Metabolites of TSNAs:			
NNAL	To be defined	To be defined	Continuous

*References for the different scores:

- CAT: The CAT has a scoring range of 0-40. See CAT User Guide & FAQs for cut-offs- MMRC: Scores from 0-4. 0 = Ich bekomme nur Atemnot bei sehr starker Belastung; [...] 4 = Ich kann wegen meiner Atemnot das Haus nicht verlassen ...

- COPD: y/n: If y: Number of COPD exacerbations/hospitalisation due to COPD and number of COPD exacerbations/hospitalisation due to COPD in last 6 months.

- ECRHS: y/n

- ACT: scoring range of 5-25. See ACT-Erwachsene 2017-08 for cut-offs.

- MINNESOTA NICOTINE WITHDRAWAL SCALE: 0 = überhaupt nicht, 1 = ganz leicht, 2 = etwas, 3 = mittel, 4 = sehr

CTU Bern	SAP for: ESTxENDS	Version: 1-02_0
----------	-------------------	---------------------------------

CTU Bern	Template: Statistical Analysis Plan (SAP)	Version: 03	
	Code: CS_STA_TEM-11	Valid from: 28.02.2019 5.6.2023	Page 15 of 27

5.5 Procedural characteristics (if applicable)

Not applicable.

5.6 Adherence and protocol deviations

Adherence

Adherence in the control group is defined as not having used an ENDS device on 5 or more days during the last 7 days of any visit.

Adherence in the intervention group is defined as having used an ENDS device on 5 or more days during the last 7 days of at least one visit.

Adherence will be presented in a table as number (and %) of patients not smoking cigarette, smoking cigarettes only, smoking ENDS only, and smoking cigarettes and ENDS for both groups at each time point (Weeks 1, 2, 4, 8, and month 6). In addition, the number (and %) of patients using any NRT (patches, gums) or other smoking cessation medication (bupropion, varenicline) during the 24 hours before the visit will be presented in a similar table.

Protocol deviations

Protocol deviations are defined in Table 1. All of these protocol deviations will be presented in a table with the number of patients (%) having a protocol deviation for the control and intervention group.

5.7 Withdrawal/follow-up

Subjects will be withdrawn from intervention, if she reports to be pregnant. A subject may be withdrawn from the intervention, when:

- he/she does not comply with instructions by the research team
- a treatment related SAE is expected
- the protocol has been irretrievably violated, as determined by the sponsor

Subjects will be withdrawn from follow-up if they withdraw consent. A subject may be withdrawn from follow-up if the responsible study investigator decides that continued participation in the study could be harmful to the subject's wellbeing.

Withdrawal from intervention or follow-up is recorded in the end of study form. The number of patients not finishing the study according to the protocol due to:

- withdrawal of consent
- lost to follow up
- exclusion by PI
- SAE
- death, and

CTU Bern	SAP for: ESTxENDS	Version: 1-02_0
----------	-------------------	---------------------------------

CTU Bern	Template: Statistical Analysis Plan (SAP)	Version: 03
	Code: CS_STA_TEM-11	Valid from: 28-02-2019 5.6.2023

- other reason

will be presented in a table for both groups and each time point (derived from lastcontact_date in end form). Other reasons will be listed as free text.

A summary of the follow-ups will present the numbers of calls performed as well as the visits performed at each time point.

CTU Bern	SAP for: ESTxENDS	Version: 1.02.0
CTU Bern	Template: Statistical Analysis Plan (SAP)	Version: 03
	Code: CS_STA_TEM-11	Valid from: 28.02.2019 5.6.2023

6. Analysis

6.1 Outcome definitions

Primary outcome: The primary outcome will be the continuous cigarette smoking abstinence from target quit date to the 6-month follow-up visit, ascertained by self-report at the 6-month follow-up exam (self-report of no smoking from target quit date) and confirmed by urinary level of anabasine (<3 ng/ml). If anabasine is missing, validation by exhaled carbon monoxide (CO). The outcome is a binary outcome.

Core secondary outcomes:

- Secondary smoking cessation outcomes to the 6-month follow-up visit:
 - Continuous smoking abstinence. Self-report of having smoked no cigarettes from TQD, validated by urinary levels of NNAL (4-(methylnitrosamino)-1-(3-pyridyl)-1-butanol). If NNAL is missing, validation by urinary levels of anabasine or exhaled CO.
 - Self-reported smoking abstinence allowing a 2-week 'grace period' after the TQD
 - Validated smoking abstinence allowing a 2-week 'grace period' after the TQD, validated by urinary levels of anabasine. If anabasine is missing validation by exhaled CO.
 - Validated smoking abstinence allowing a 2-week 'grace period' after the TQD, validated by urinary levels of NNAL. If NNAL is missing, validation by urinary levels of anabasine or exhaled CO.
 - Self-reported smoking abstinence allowing up to 5 cigarettes in total after the TQD.
 - Validated smoking abstinence allowing up to 5 cigarettes in total after the TQD, validated by urinary levels of anabasine. If anabasine is missing validation by exhaled CO.
 - Validated smoking abstinence allowing up to 5 cigarettes in total after the TQD, validated by urinary levels of NNAL. If NNAL is missing, validation by urinary levels of anabasine or exhaled carbon monoxide (CO).
 - Self-reported 7-day point prevalence abstinence at 6 months, Self-report of having smoked no cigarettes in the past seven days.
 - Validated 7-day point prevalence abstinence. Confirmation of having smoked no cigarettes in the past seven days, validated by urinary levels of anabasine. If anabasine is missing validation by exhaled carbon monoxide (CO).
 - Validated 7-day point prevalence abstinence. Confirmation of having smoked no cigarettes in the past seven days, validated by urinary levels of NNAL. If NNAL is missing, validation by urinary levels of anabasine or exhaled carbon monoxide (CO).

CTU Bern	SAP for: ESTxENDS	Version: 4.02.0	
CTU Bern	Template: Statistical Analysis Plan (SAP)	Version: 03	
	Code: CS_STA_TEM-11	Valid from: 28.02.2019 to 06.2023	Page 18 of 27

- Number of cigarettes smoked per day (CPD), self-reported, at baseline, TQD, phone visits and 6 months visit
- Change in number of cigarettes smoked per day (CPD), self-reported. Successful reduction defined as 50% reduction in CPD.
- Respiratory symptoms assessed by questionnaires:
 - Change in COPD Assessment Test (CAT) from baseline to month 6, score from 0-40 (regarded as continuous)
- Change in cardiovascular risk factors from baseline to month 6, assessed by
 - Total cholesterol (continuous)
 - HDL-cholesterol (continuous),
 - LDL-cholesterol (calculated, continuous),
 - triglycerides (continuous),
 - blood pressure levels (continuous),
 - heart rate (continuous),
 - waist circumference (continuous) and
 - body mass index (continuous).
- AEs (in categories from adjudication committee)
- SAEs (in categories from adjudication committee)

6.2 Derivation of Outcomes

Comments to secondary smoking cessation outcomes:

- Smoking is allowed during the grace period.
- The number of cigarettes smoked since the last visit is recorded as a categorical variable (1-5 cigarettes, >5 cigarettes). If the participant smoked more than once a day cigarettes in the last 7 days, the value is recorded as numeric variable. For secondary smoking cessation outcomes, we will assume the median value for the categorical variable. I.e. if a subject records 2 times to smoke 1-5 cigarettes, we assume him to be over the limit of 5 cigarettes.

Table 3: Derivation of primary and secondary outcomes.

Outcome	eCRF sheet	Variable	Variable type	Derivation	Outcome type
Primary: continuous smoking abstinence from target quit date to the 6-month follow-up visit AND	cig_ecig	quit_smoke_again	Binary: No, Yes	{ [Week 1/2/4/8, and month 6] quit_smoke_again == No AND quit_tobacco_inhale ==	Binary
		quit_tobacco_inhale	Binary: No, Yes		
	cig_ecig_6m	quit_smoke_again	Binary: No, Yes		
		quit_tobacco_inhale	Binary: No, Yes		

CTU Bern	SAP for: ESTxENDS	Version: 1-02.0
-----------------	-------------------	---------------------------------

CTU Bern	Template: Statistical Analysis Plan (SAP)	Version: 03
	Code: CS_STA_TEM-11	Valid from: 28-02-2019 to 05-06-2023

urinary level of anabasine (<3 ng/ml) OR	to be defined	to be defined	to be defined	No} AND {x < 3 if x!=missing, vs_co2_level<10 if x==missing & vs_co2_level ==missing}
CO level	vital_6m	vs_co2_level	Continuous	
Secondary outcomes				
continuous smoking abstinence from target quit date to the 6-month follow-up visit AND	Cig_ecig, cig_ecig_6m	quit_smoke_again, quit_tobacco_inhale	Binary: No, Yes, Binary:No, Yes	{[Week 1/2/4/8, and month 6] quit_smoke_again == No AND quit_tobacco_inhale == No} AND
urinary level of NNAL (<10 pg/ml creat) OR	To be defined	To be defined	To be defined	{y < 10 if y!=missing, x<3 if y==missing & x!=missing, vs_co2_level<10 if y==missing & x==miss- ing & vs_co2_level!=missing }
urinary level of anabasine (<3 ng/ml) OR	To be defined	To be defined	To be defined	
CO level	Vital, Vital_6m	vs_co2_level	continuous	
Continuous smoke abstinence allowing a 2-week grace period after TQD	cig_ecig / cig_ecig_6m	quit_smoke_again quit_tobacco_inhale	Binary: No, Yes	[Week 4, Week 8, and 6 months] sum(quit_smoke_again == No) >= 2 AND sum(quit_tobacco_in- hale == No) >= 2
Continuous smoke abstinence allowing a 2-week grace period after TQD AND	cig_ecig / cig_ecig_6m to be defined	quit_smoke_again quit_tobacco_inhale quit_smoke_n	Binary: No, Yes Binary: No, Yes categorical: 1-5 cigarettes, > 5 cigarettes	{[Week 4, Week 8, and 6 months] sum(quit_smoke_again == No) >= 2 AND sum(quit_tobacco_in- hale == No) >= 2 AND sum(quit_smoke_n == 1-5) <= 1} AND { x < 3 if x!=missing, vs_co2_level<10 if x==missing & vs_co2_level ==missing}
urinary level of anabasine (<3 ng/ml) OR	To be defined	To be defined	To be defined	
CO level	Vital, Vital_6m	vs_co2_level	continuous	
Continuous smoke abstinence allowing a 2-week grace period after TQD AND	cig_ecig / cig_ecig_6m to be defined	quit_smoke_again quit_tobacco_inhale quit_smoke_n	Binary: No, Yes Binary: No, Yes categorical: 1-5 cigarettes, > 5 cigarettes	{[Week 4, Week 8, and 6 months] sum(quit_smoke_again == No) >= 2 AND sum(quit_tobacco_in- hale == No) >= 2 AND sum(quit_smoke_n == 1-5) <= 1} AND { y < 10 if y!=missing, x<3 if y==missing & x!=missing, vs_co2_level<10 if
urinary level of NNAL (<10 pg/ml creat) OR	To be defined	To be defined	To be defined	
urinary level of anabasine (<3 ng/ml) OR	To be defined	To be defined	To be defined	

CTU Bern	SAP for: ESTxENDS	Version: 1.02.0
----------	-------------------	---------------------------------

CTU Bern	Template: Statistical Analysis Plan (SAP)	Version: 03
	Code: CS_STA_TEM-11	Valid from: 28.02.2019 to 05.06.2023

CO level	Vital, Vital_6m	vs_co2_level	continuous	y==missing & x==missing & vs_co2_level!=missing }	
Self-reported smoking abstinence allowing up to 5 cigarettes in total after the TQD	cig_ecig / cig_ecig_6m	quit_smoke_n	categorical	sum(quit_smoke_n == 1-5) <= 1	Binary
Self-reported smoking abstinence allowing up to 5 cigarettes in total after the TQD AND	cig_ecig / cig_ecig_6m	quit_smoke_n	Categorical	sum(quit_smoke_n == 1-5) <= 1 AND	Binary
urinary level of anabasine (<3 ng/ml) OR	To be defined	To be defined	To be defined	{ x < 3 if x!=missing, vs_co2_level<10 if x==missing & vs_co2_level ==missing}	
CO level	Vital, Vital_6m	vs_co2_level	continuous		
Self-reported smoking abstinence allowing up to 5 cigarettes in total after the TQD AND	cig_ecig / cig_ecig_6m	quit_smoke_n	Categorical	sum(quit_smoke_n == 1-5) <= 1 AND	Binary
urinary level of NNAL (<10 pg/ml creat) OR	To be defined	To be defined	To be defined	{ y < 10 if y!=missing, x<3 if y==missing & x!=missing, vs_co2_level<10 if y==missing & x==missing & vs_co2_level!=missing }	
urinary level of anabasine (<3 ng/ml) OR	To be defined	To be defined	To be defined		
CO level	Vital, Vital_6m	vs_co2_level	continuous		
Self-reported 7-day point prevalence abstinence at 6 months	cig_ecig_6m	quit_smoke_again, quit_smoke_7days	Binary: No, Yes	quit_smoke_again == No AND quit_smoke_7days == No	Binary
Self-reported 7-day point prevalence abstinence at 6 months AND	cig_ecig_6m	quit_smoke_again, quit_smoke_7days	Binary: No, Yes Binary: No, Yes	{ quit_smoke_again == No AND quit_smoke_7days == No} AND { x < 3 if x!=missing, vs_co2_level<10 if x==missing & vs_co2_level ==missing}	Binary
urinary level of anabasine (<3 ng/ml) OR	To be defined	To be defined	To be defined		
CO level	Vital, Vital_6m	vs_co2_level	continuous		
Self-reported 7-day point prevalence abstinence AND	cig_ecig_6m	quit_smoke_again, quit_smoke_7days	Binary: No, Yes	{quit_smoke_again == No AND quit_smoke_7days == No} AND	Binary
urinary level of NNAL (<10 pg/ml creat) OR	To be defined	To be defined	To be defined	{y < 10 if y!=missing, x<3 if y==missing & x!=missing, vs_co2_level<10 if	
urinary level of anabasine (<3 ng/ml) OR	To be defined	To be defined	To be defined		

CTU Bern	SAP for: ESTxENDS	Version: 4.02.0
----------	-------------------	---------------------------------

CTU Bern	Template: Statistical Analysis Plan (SAP)	Version: 03
	Code: CS_STA_TEM-11	Valid from: 28.02.2019 5.6.2023

CO level	Vital, Vital_6m	vs_co2_level	continuous	y==missing & x==missing & vs_co2_level!=missing}	
Number of cigarettes smoked per day (CPD)	cig_ecig / cig_ecig_6m	quit_more1perday	continuous (number of cigarettes per day in the last 7 days)	[BL, TQD, phone visits and 6-month visit] quit_more1perday	Continuous
Change in the self-reported number of cigarettes smoked per day in the last 7 days	cig_ecig / cig_ecig_6m	quit_more1perday	continuous (number of cigarettes per day in the last 7 days)	(quit_more1perday[month 6] / quit_more1perday[day 0]) >= 0.5 IF [month 6]{contact_estab_yn == Yes AND quit_smoke_again == Yes AND quit_smoke_7days == Yes AND quit_smoke_nperday == ">=1x/Tag"} ELSE TRUE	Binary
CAT	cat / cat_6m	q1 to q8	radio (0 to 5)	sum(q1 to q8)[cat_6m] – sum(q1 to q8)[cat]	continuous (score scale 0-40, difference can be 0-40 as well)
Cholesterin (total)	vital vital_6m	lab_choles_total	continuous (mmol/L)	lab_choles_total[vital_6m] – lab_choles_total[vital]	continuous (mmol/L)
LDL cholesterol	calculated	calculated	Continuous (mmol/L)	lab_choles_total[vital_6m]-lab_choles_hdl[vital_6m]- (lab_triglyceride[vital_6m] /5)-lab_choles_total[vital]-lab_choles_hdl[vital]- (lab_triglyceride[vital] /5) [Friedewald formula]	continuous (mmol/L)
HDL cholesterol	vital vital_6m	lab_choles_hdl	continuous (mmol/L)	lab_choles_hdl[vital_6m] – lab_choles_hdl[vital]	continuous (mmol/L)
triglycerides	vital vital_6m	lab_triglyceride	continuous (mmol/L)	lab_triglyceride[vital_6m] - lab_triglyceride[vital]	continuous (mmol/L)
blood pressure	vital vital_6m	vs_bpressure_sys1-3, vs_bpressure_dias1-3	continuous (mmHg)	mean(vs_bpressure_sys1-3), mean(vs_bpressure_dias1-3)	continuous (mmHg)
heart rate (mean of the second and third measure)	vital vital_6m	vs_heart_rate_2 vs_heart_rate_3	continuous (bpm)	mean(vs_heart_rate_2, vs_heart_rate_3)[vital_6m] – mean(vs_heart_rate_2, vs_heart_rate_3)[vital]	continuous (bpm)
waist circumference	vital vital_6m	vs_waist_cm	continuous (cm)	vs_waist_cm[vital_6m] - vs_waist_cm[vital]	continuous (cm)
BMI	vital vital_6m	bmi	continuous (kg/m ²)	bmi[vital_6m] – bmi[vital]	continuous (kg/m ²)
Lab values					
Metabolites of nicotine:					

CTU Bern	SAP for: ESTxENDS	Version: 4.02.0
----------	-------------------	---------------------------------

CTU Bern	Template: Statistical Analysis Plan (SAP)	Version: 03	
	Code: CS_STA_TEM-11	Valid from: 28.02.2019 5.6.2023	Page 22 of 27

Anabasine	To be defined	To be defined	dichotomized at <3 ng/ml	anabasine < 3	Binary: <3ng/ml, ≥3ng/ml
Metabolites of TSNAs:					
NNAL	To be defined	To be defined	dichotomized at <10pg/ml	NNAL < 10	Binary: <10pg/ml, ≥10pg/ml

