5. STUDY OUTCOMES

5.1 Primary Outcome

The primary outcome for the main analysis at 6-months follow-up will be the continuous smoking abstinence from target quit date (TQD) to the 6-month follow-up visit, ascertained by self-report (self-report of no smoking from target quit date) and confirmed by urinary level of anabasine (<3 ng/ml).^{1, 34, 35} If anabasine is missing, validation will be done by exhaled carbon monoxide (CO) (<10 ppm).

The primary outcome for the extended follow-ups at 12- and 24-months will be the self-reported 7-day point prevalence abstinence (not having smoked cigarettes within the preceding week), again confirmed by urinary level of anabasine (<3 ng/ml). If anabasine is missing, validation by exhaled carbon monoxide (CO) (<10 ppm).

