9.2.1 Assessment of primary outcome

- The primary outcome at 6-month will be the continuous smoking abstinence from target quit date to the 6-month follow-up visit, ascertained by self-report at the 6-months visit (self-report of no smoking from target quit date) and confirmed by urinary level of anabasine (<3 ng/ml). Complete Urine samples will be collected in a flask. The laboratory in Lausanne (Unisanté, Centre universitaire de médecine générale et santé publique, Lausanne) has a routine analytical method for measuring nicotine metabolites in urine and participates regularly in external quality control testing.
- The primary outcome at 12- and 24- months follow-up will be the self-reported 7-day point prevalence abstinence (not having smoked cigarettes within the preceding week), confirmed by urinary level of anabasine (<3 ng/ml).

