October 10 th , 2019 / November 26 th 2019	Approval of changes: 
 1. Study site Zürich (Nov 26th) and St-Gallen (Oct 10th). 2. Extension of follow-up to 12- and 24-months. 3. Vouchers to control group given at baseline instead of giving them the voucher after completion of the 6-months visit. 4. Adaptations of documentation of Adverse Events 	Protocol version 7.0, Dated September 10 th , 2019. 
 1. Extension of recruitment to study site Zürich and St-Gallen to meet recruitment targets. 2. Additional funding obtained by Tobacco Prevention Fund and Swiss Cancer Research enabling extension of follow-up to 12- and 24-months follow-up 3. We noticed selective attrition through withdrawal in the control group. We decided the control group should receive a voucher at baseline instead of 6-months follow-up to mitigate deception in control group. 4. Further adaptations in documentation of AE by study nurses with systematic queries to hospitals and attending physicians in case of AE and not only SAE
October 11 th , 2019	Information to CEC related to EVALI epidemic in USA: 
 1. Letter sent to all participants asking them to report any respiratory symptoms 	
 1. In light of the reports in the USA about EVALI cases, the research team reviewed already collected SAE and AE, reviewed the literature and reports coming out of the USA and decided to pursue the study as planned. We sent a letter to participants informing them about the situation in the USA, which was most likely due to use of illicit e-liquids or e-liquids used for vaping cannabis and that they should continue to report adverse events to study nurses. 2.
March 2020, until July 2020	Incremental lockdown measures related to COVID pandemic decided by Federal Council of Switzerland. 
 1. Pause in recruitment of new participants from: March to July 2020 2. Shift as much as possible clinical follow-up visit from in-person visits to phone follow-ups. 	
 1. COVID pandemic required us to pause recruitment of new participants. 2. Study nurses continued to follow-up participants at scheduled times over the phone, following up participants in person if allowed locally.

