2.7 Timing of outcome assessments

Study visits are scheduled at baseline and at 6 months (180 days – 4 weeks / + 12 weeks). Telephone visits are scheduled at target quit date (Day 0), Week 1 (7 ± 2 days), Week 2 (14 ± 3 days), Week 4 (28 ± 4 days), and Week 8 (56 ± 7 days).

The primary outcome is assessed at month 6 and needs to be derived from all telephone visits as well as the month 6 follow-up visit.

Secondary outcomes are assessed at months 6.

Further, outcomes are assessed at 12, and 24 months. These outcomes are not part of the current SAP.

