4.3 Estimands

4.3.1 Treatment policy estimand

Outcome of interest: The primary analysis of the primary outcome (binary) will focus on the treatment policy estimand,

Patient set of interest: using the full analysis set following the intention-to-treat principle, i.e. subjects will be analysed according to the randomized group, irrespective of the treatment actually received.

Intercurrent events: Intercurrent events will be disregarded. Missing values in the primary outcome will be categorized as persistent smoker (i.e. treatment failures).

Summary measure: The difference between the two groups will be presented as a relative risk.

The primary analysis of secondary outcomes will focus on the treatment policy estimand as well. Missing values in secondary smoking cessation outcomes will be treated as for the primary outcome. Missing values in other outcomes will be imputed. Effect sizes of binary outcomes will be presented as relative risk. Effect sizes of continuous outcomes will be presented as mean difference.

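### SAP 2.0 Table 3 never lets exhaled CO confirm abstinence, and its every-call self-report rule for the primary outcome conflicts with the month-6 definition elsewhere

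*Supplement*

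**What the plan says.** Four places in the latest documents define the 6-month primary outcome.

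- **Validation, in words.** SAP 2.0 section 6.1: "If anabasine is missing, validation by exhaled carbon monoxide (CO"). Protocol 9.0 section 5.1: "If anabasine is missing, validation will be done by exhaled carbon monoxide (CO) (<10 ppm").
- **Validation, as derived.** SAP 2.0 section 6.2, Table 3, primary row, where x is anabasine: "vs_co2_level<10 if x==missing & vs_co2_level ==missing". The anabasine-validated rows for the grace period, up to 5 cigarettes and 7-day abstinence carry the same condition. The NNAL-validated rows use `!=missing` for CO.
- **Self-report, in words.** Protocol section 9.2.1: "ascertained by self-report at the 6-months visit (self-report of no smoking from target quit date"). SAP 6.1 likewise takes it at the 6-month examination.
- **Self-report, as derived.** SAP 2.7 says the outcome "needs to be derived from all telephone visits as well as the month 6 follow-up visit". Table 3 requires 'No' to both smoking items at weeks 1, 2, 4, 8 and month 6.

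On missing outcomes, SAP 4.3.1 states: "Missing values in the primary outcome will be categorized as persistent smoker (i.e. treatment failures"), and SAP 6.5 repeats it. Neither SAP Table 4 nor the closing list of adjustments to the SAP touches any of this.

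**The concern.** The derivation table is what a programmer follows, and here it does not implement the endpoint described in the text.

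First, the fallback marker is unusable. The branch opens only when CO is absent, so CO can never confirm abstinence.

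Second, there are two self-report definitions. One is recall at month 6 of no smoking since the target quit date. The other is a run of five negative answers. They give the same result only if every call was made. Protocol 7.4 expects that some participants will not be reached by phone and keeps them in the trial, but no rule says how a missed call enters the derivation.

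What is at stake is the count of quitters for the 6-month primary outcome, on which the sample size rests.

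**Working it through.** **1. The validation rule, case by case** (self-report of abstinence taken as given)

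| Anabasine | CO | Table 3 as written | SAP 6.1 and Protocol 5.1 |
|---|---|---|---|
| measured | any | decided by anabasine <3 | same |
| missing | measured, <10 | no branch applies; counted as smoker | abstinent |
| missing | measured, ≥10 | no branch applies; counted as smoker | smoker |
| missing | missing | tests whether a missing value is below 10; false in Stata, which ranks missing above any number; smoker | not validated; smoker |

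Only the second line changes when `==missing` becomes `!=missing`.

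**2. The self-report rule.** A missing answer is not equal to 'No', so a participant with one missed call fails the Table 3 condition. If the outcome is instead treated as missing, SAP 6.5 codes it as smoking. Either route gives the same result, although the SAP does not say so outright. By contrast, the grace-period rows accept two 'No' answers out of three visits; the primary row has no such tolerance.

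**3. The plan's own figure.** Protocol 11.2 gives 12% v 19%, two-sided alpha 0.05 and 90% power. With unpooled variance:

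n = (1.960 + 1.282)² × (0.12×0.88 + 0.19×0.81) / 0.07² = 557 per arm, as stated.

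**4. Power after loss of abstainers.** With n = 586 per arm and p̄ the mean of p₁ and p₂:

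- SE₀ = √(2p̄(1−p̄)/n)
- SE₁ = √((p₁(1−p₁) + p₂(1−p₂))/n)
- power = Φ((p₂ − p₁ − 1.96·SE₀)/SE₁)

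Base case: SE₀ = 0.02114, SE₁ = 0.02104, z = (0.07 − 0.04144)/0.02104 = 1.357, power 91.3%.

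The documents do not give the share of true abstainers who are lost. The shares below are assumed, are equal in both arms, and suppose that no smoker is counted as abstinent.

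| Abstainers lost | Control | ENDS | Difference (points) | Power |
|---|---|---|---|---|
| 0% | 12.0% | 19.0% | 7.0 | 91.3% |
| 5% | 11.4% | 18.1% | 6.7 | 89.6% |
| 10% | 10.8% | 17.1% | 6.3 | 87.6% |
| 20% | 9.6% | 15.2% | 5.6 | 82.9% |

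The relative risk stays at 19/12 = 1.58 throughout.

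**5. What missed calls could contribute.** If each of four calls is missed with probability q, independently, the share missing at least one is 1 − (1−q)⁴: 7.8% for q = 2%, 18.5% for 5%, 34.4% for 10%. At 34.4% power would be about 74%. If the same people miss all their calls, the share is only q. Both q and the independence are assumptions.

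**6. Unequal loss.** Losing 20% of control and 10% of ENDS abstainers gives 9.6% v 17.1%, RR 1.78. Losing 10% and 20% gives 10.8% v 15.2%, RR 1.41. The error can move the estimate either way from 1.58.

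**The case against.** The strongest reply on CO is that the operator is an obvious slip. Taken literally the condition can never be met, and SAP 6.1, Protocol 5.1 and the NNAL rows all show what was meant. SAP 6.9 also provides for double programming. CO and anabasine are collected at the same visits, and a month-6 contact held by phone would usually lose both, which is failure under either rule. All this makes harm less likely and the affected group perhaps small. It does not remove the fault: the condition stands in four rows of the latest SAP, and a second programmer working from the same table could repeat it.

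On self-report, using the calls is deliberate and defensible. Table 3's notes say cigarettes are recorded since the last visit, so serial answers may be how continuous abstinence is built. Nor does the SAP state that a missed call means smoking. Both points stand. What remains is that the sections disagree and the missed call has no rule.

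A reader might go further and infer bias in favour of ENDS, with an inflated false-positive rate. The history of changes does record: "We noticed selective attrition through withdrawal in the control group". The trial is open label, and only ENDS participants use the calls for device support and e-liquid orders. But that entry concerns withdrawal. Participants without month-6 data are failures under either rule, so it says nothing about abstainers who attended at month 6 and had missed a call. The same entry moves the control voucher to baseline in response, and both arms receive counselling at every call. Any false-positive figure would need an assumed difference in missed calls between arms and an assumed pattern within persons; the documents supply neither.

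**Conclusion.** The concern holds as a defect in the written derivation. Table 3 contradicts SAP 6.1 and Protocol 5.1 on the CO fallback, in the primary row and three secondary rows. Table 3 and SAP 2.7 conflict with SAP 6.1 and Protocol 9.2.1 on self-report. That a missed call counts as smoking is a literal reading combined with SAP 6.5, not an explicit instruction.

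The demonstrable effect is loss of true abstainers, and with it power: from about 91% to between 90% and 83% if 5% to 20% are affected equally. The harm arises only if the table is programmed as written. Whether the arms would be affected differently, and in which direction, cannot be determined from the documents.

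The point concerns the 6-month primary outcome. It should not be read as touching the trial's only primary endpoint, since Protocol 5.1 names separate ones at 12 and 24 months, which this SAP leaves out. Nor is it a criticism of how absent month-6 data are handled in general: the available-case analysis in SAP 6.3.3 and the censoring weights in SAP 6.5 address that. They do not repair this rule, because neither says whether the participants at issue count as missing or as observed smokers.

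**What to change.** 1. In SAP Table 3, in the primary row and the three anabasine-validated secondary rows, write `vs_co2_level<10 if x==missing & vs_co2_level!=missing`, and state that both markers missing counts as failure.
2. Reconcile SAP 2.7, SAP 6.1 and Table 3 on one self-report rule: the month-6 report of no smoking since the target quit date defines it; a recorded 'Yes' at any completed call disqualifies; a call that was not made does not.
3. Where code already exists, check which rule it follows. A count by arm of participants whose status changes would show whether the matter was material.

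The cost is SAP wording and a few lines of code, with no new data.
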